### *3.1. Study Design*

A home-based, randomized, single-blind and crossover trial included 14 adolescents aged 14-18 years with type 1 diabetes. All participants were sent to their homes for 4 consecutive days with a different glycemic index breakfast. The insulin doses of the meals were calculated according to CC and FII methods. Test breakfasts with different GIs and insulin requirements calculated with different algorithms are as follows: High GI calculated by CC (CHGI), low GI calculated by CC (CLGI), high GI calculated by FII (FHGI) and low GI calculated by FII (FLGI). The order of the test meals and insulin algorithms was determined by using a computer-generated randomization sequence before recruitment. The test diets prepared by the dietitian were given to the participants by the diet company before the test day. Test meals were served as a breakfast after 8-hours fasting and participants were asked to consume the meal in full, within 20 min. The breakfast plates were collected and weighed after the test day. On the day before each test meal, participants were instructed to eat an evening snack meal at 22:00 h and to refrain from eating and/or drinking (except for water) and/or doing any physical activity beyond that of their typical daily activities. Participants started to consume test meals at 07.00 h. They were asked not to consume any food other than breakfast for postprandial 240 min. Participants maintained their normal activity levels during the study days. The classification of meals according to insulin dose calculation methods is shown in the Figure 1.

This study was conducted according to the guidelines laid down in the Declaration of Helsinki. The Clinical Research Ethics Committee of the Erciyes University approved the protocol (2018/607) on 21 November 2018, and all participants gave written informed consent.

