### 4. Measurement of blood glucose

Postprandial glycemia was measured for 240 min with both continuous glucose monitoring and glucometer. Participants attended the clinic prior one day of the study for insertion of CGM (Medtronic iPro2) (11). CGM data was download and reviewed after completion of the study. Capillary blood testing was performed just before breakfast (t=0 min) and at time points 30, 60, 90, 120, 150, 180, 210 and 240 min after the meal with glucometer (Accu-Check Performa Nano) (8, 11). Participants were also required to keep these blood glucose values.

Hypoglycaemic event, defined as a blood glucose level drop to  $< 3.9$  mmol/l (30), confirmed on fingerstick. Data was excluded for the times after the participant had a hypoglycaemic event for the rest of the study period (11).

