### *6. Statistical Analysis*

Statistical analysis was performed using the Statistical Package for the Social Sciences (version 22.0; IBM SPSS Statistics) software. Data were expressed as the number (n) and percentage (%) for categorical variables, and means  $\pm$  SDs, medians (25th-75th percentiles) for continuous variables. Normality was assessed using the Shapiro- Wilk test. Furthermore, continuous variables were examined for skewness and kurtosis, and log-transformed before analysis and reported back-transformed geometric means (G)  $\pm$  standard error (S.E) when required (33). Differences between groups were tested using t-tests. The blood glucose profile during the 4-h postprandial period was quantified as area under the curve (AUC) calculated according to the trapezoidal rule. A one-way repeated measure was used to analyse between the comparable test conditions. For all statistical analyses, p values less than 0.05 were considered to have statistical significance (8).

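### The AUC comparison has no rule for a missing test day; read as a classical four-condition repeated-measures analysis, one unusable day also discards that participant's other three days, and a mixed model would keep them.

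*Combined protocol and SAP*

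**What the plan says.** Section 3.1 (Study Design) describes the trial: "A home-based, randomized, single-blind and crossover trial included 14 adolescents aged 14-18 years with type 1 diabetes". The four conditions cross two dosing methods (CC, FII) with two breakfasts (high and low GI) and are tested at home: "All participants were sent to their homes for 4 consecutive days with a different glycemic index breakfast".

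Section 6 (Statistical Analysis) sets the outcome: "The blood glucose profile during the 4-h postprandial period was quantified as area under the curve (AUC) calculated according to the trapezoidal rule". Two comparisons are named: "Differences between groups were tested using t-tests" and "A one-way repeated measure was used to analyse between the comparable test conditions". The software is SPSS 22.0, but the procedure within it is not named. The plan does not list which conditions count as comparable, and it does not say whether the t-tests are paired.

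Section 4 (Measurement of blood glucose) adds an exclusion: "Data was excluded for the times after the participant had a hypoglycaemic event for the rest of the study period".

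The documents define neither a usable AUC nor an analysis population. They give no rule for a missed or incomplete test day, and no sample-size calculation or dropout allowance.

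**The concern.** A classical one-way repeated-measures analysis needs one value per condition from every participant. Anyone with a gap is dropped, together with the days that were measured successfully. With 14 participants, each such loss is 1/14 = 7.1% of the sample.

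Days can be lost in ordinary ways: withdrawal, illness, a meal not eaten, failed readings, or a curve cut too short to score. Testing is unsupervised at home on consecutive days, and no replacement day is described.

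The first thing at stake is precision. The second is who remains: if participants stop after a bad day, a complete-case set is selected by what happened after randomisation. The point concerns which data enter the analysis. Which factors the model should contain, and how a shortened curve is scored, are separate questions, although the second must be answered before this fix can be applied.

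**Working it through.** **Inputs from the documents.** 14 participants and 4 test days each (section 3.1), so 14 × 4 = 56 planned days; one AUC per day (section 6). The figure of 14 comes without any calculation, so there is no stated result to reproduce.

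**Assumed, because the documents give nothing.** A probability q that a test day is unusable, independent between days, at 5%, 10% and 20%; equal variances and equal within-person correlation, 0.3 to 0.6.

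**Step 1: one unusable day.**
- Mixed model: 56 − 1 = 55 days analysed.
- Classical analysis, four conditions: 13 × 4 = 52 days, so 55 − 52 = 3 usable days discarded. Error degrees of freedom fall from (14 − 1)(4 − 1) = 39 to (13 − 1)(4 − 1) = 36.
- Pairwise comparison: 13 of 14 pairs remain, and one usable partner day is discarded from that comparison.

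In a trial run on artificial data (Python statsmodels, not SPSS), the classical routine refused a data set with one of 56 cells empty. It ran only after the participant was removed (52 rows); a mixed model used 55.

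**Step 2: expected losses.** Complete participants = 14(1 − q)⁴; complete pairs = 14(1 − q)²; days analysed = 56(1 − q)⁴ for complete cases and 56(1 − q) for all available days.

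| q | Complete on 4 days | Complete pairs | Days, complete case | Days, all available |
|---|---|---|---|---|
| 5% | 11.4 | 12.6 | 45.6 | 53.2 |
| 10% | 9.2 | 11.3 | 36.7 | 50.4 |
| 20% | 5.7 | 9.0 | 22.9 | 44.8 |

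**Step 3: standard error of the CC-FII contrast** (mean of the two FII conditions minus mean of the two CC conditions). With n complete participants its variance is σ²(1 − ρ)/n. With all available days it is the generalised least-squares variance, computed for each simulated pattern of missing days. The ratio of standard errors, complete case to all available, is:

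| q | Four-condition reading | Pairwise reading |
|---|---|---|
| 5% | about 1.08 | about 1.02 |
| 10% | about 1.17 | 1.04-1.05 |
| 20% | about 1.38-1.43 | 1.09-1.11 |

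The ranges reflect the correlation and the way the ratio is averaged over patterns. The pairwise column compares one pair of conditions with the mixed model's estimate of the same difference. As a rough check on the four-condition column, the square root of the ratio of days analysed is (1 − q)^(−1.5): 0.95^(−1.5) = 1.08, 0.90^(−1.5) = 1.17 and 0.80^(−1.5) = 1.40.

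**Step 4: bias.** Simulated with correlation 0.5 and a true FII − CC difference of −0.50 SD; the threshold for a low day, 1.3 SD below the CC mean, is also assumed.
- Participants stop after a low day: the mixed model recovers −0.50; complete-case estimates lie between −0.41 and −0.46.
- A day is lost because its own value is low: complete case gives −0.42, the mixed model −0.37. Both are biased, the mixed model slightly more.

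**The case against.** **The complete-case rule is inferred.** A reader might take section 6 to say that only participants with four usable days are analysed. It does not say so. It names no procedure, and a repeated-measures analysis can be fitted in SPSS as a mixed model. It speaks of comparable conditions, which may mean two at a time, for example the two dosing methods within one breakfast. This stands: the four-condition loss is conditional on one reading, and the pairwise penalty is much smaller.

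**No lost day is documented.** The text is in the past tense, gives 14 participants and mentions no withdrawal. One might infer that days were lost, or that 14 is what remained after dropout; the documents support neither. With no lost days the two approaches use the same data.

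**The hypoglycaemia exclusion need not remove a day.** A reader might infer that every hypoglycaemic event costs a test day, or all later ones. Section 4 excludes the times after the event, so on the within-morning reading it shortens a curve and keeps the earlier part. The study period in that sentence could also mean the remaining test days; the text does not settle this. Nor need one failed device lose the day, because glucose is measured both by continuous monitoring and by glucometer.

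**A mixed model does not cure the selection.** It is tempting to present the change as removing bias from participants who go low. Step 4 shows that this holds only when loss depends on earlier observed days.

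What the objections leave intact is that the plan names a repeated-measures comparison and no method for a gap. On the natural reading, usable data are discarded.

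**Conclusion.** The concern holds in conditional form. If section 6 means a classical analysis across all four conditions, each participant with a single unusable day takes three usable days out of the comparison. At assumed losses of 5%, 10% and 20% per day, the standard error of the CC-FII contrast is about 8%, 17% and 38-43% larger than it need be. If pairs are meant, the penalty is about 2%, 4-5% and 9-11%. All these figures rest on assumed rates, independence between days and equal correlation; the 20% row has no anchor in the documents.

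The case for change rests mainly on precision in a trial of 14, and secondarily on loss that follows an earlier observed day. It does not rest on a claim that the planned comparison is known to be biased. The change is still worth making, because it costs little and, with complete data, analyses the same days.

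**What to change.** In section 6, replace the one-way repeated-measures analysis of AUC with a linear mixed model: condition as fixed effect, participant as random effect, fitted by REML with a small-sample degrees-of-freedom correction (for example Satterthwaite), including every participant with at least one usable test day.

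Before that, set the rule for scoring a shortened curve and define a day as usable when its AUC can be calculated under that rule. State also whether the exclusion in section 4 ends with the same morning's 240 minutes or extends to later test days.

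Report the number of unusable days by condition and reason, and show a complete-case analysis as a sensitivity check.

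The cost is a few sentences in sections 4 and 6 and one extra analysis; no new data are needed. The downside is the missing-at-random assumption: the model does not remove, and can slightly worsen, bias when a day is lost because of that day's own low glucose. The counts by condition and the sensitivity analysis let a reader judge how much that matters.

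### The crossover analysis has no test-day term: a day effect, if there is one, would cost precision and could by chance shift the CC-FII estimate

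*Combined protocol and SAP*

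**What the plan says.** Section 3.1 (Study Design) describes a "randomized, single-blind and crossover trial included 14 adolescents aged 14-18 years with type 1 diabetes". Testing runs without a gap: "All participants were sent to their homes for 4 consecutive days". The four conditions cross two dosing algorithms (CC, FII) with two GI levels. On order, the section says: "The order of the test meals and insulin algorithms was determined by using a computer-generated randomization sequence before recruitment". It names no Latin square, Williams design or blocking.

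Section 4 (Measurement of blood glucose) places sensor insertion just before testing: "Participants attended the clinic prior one day of the study for insertion of CGM". Capillary readings are also taken at nine time points per test.

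Section 6 (Statistical Analysis) summarises each 4-hour profile as an AUC. The comparisons are then given in two sentences: "Differences between groups were tested using t-tests" and "A one-way repeated measure was used to analyse between the comparable test conditions". Day (period) and sequence are not mentioned there or elsewhere. No sample-size or power calculation is given.

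**The concern.** A one-way repeated-measures analysis has condition as its only factor. It removes differences between participants but not differences between days. In a crossover on four back-to-back days, readings might change with day for several reasons: sensor age, practice with a demanding home schedule, or after-effects of the previous day. If they do, two things follow.

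- **Precision.** Day-to-day variation goes into the error term, so the standard error grows and power falls.
- **Chance imbalance.** In the one order list actually used, FII may fall later or earlier on average than CC. Part of the day effect is then read as an algorithm difference.

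With 14 participants there is little room to absorb either.

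**Working it through.** **Inputs from the documents:** 14 participants, 4 conditions (2 algorithms x 2 GI levels), 4 consecutive days, random order, significance at p < 0.05. **Assumed:** two-sided testing, independently drawn orders for each participant, within-participant SD = 1, a linear drift common to all participants, and a true FII-minus-CC effect of 0 or 0.8 SD. The plan gives no AUC SD, effect size or power, so it has no figure to reproduce.

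**1. Degrees of freedom.** 14 x 4 = 56 AUCs. Condition-only model: 55 - 13 - 3 = 39 residual df. With day: 39 - 3 = 36.

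**2. Balance.** 14/4 = 3.5, so no list puts each condition equally often on each day. A 7:7 split of FII and CC on every day is possible. With independent random orders it occurs in about 1% of lists, while about 48% have at least one day split 10:4 or worse.

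**3. Difference in mean test day.** A day drawn from 1-4 has variance 1.25. Two different days in the same participant have covariance -1.25/3 = -0.417.

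- Two single conditions: SD = sqrt[(2 x 1.25 + 2 x 0.417)/14] = sqrt(3.333/14) = 0.49 day.
- FII versus CC: the two FII days sum to S and the two CC days to 10 - S, so the difference in means is S - 5. SD = sqrt[(2 x 1.25 - 2 x 0.417)/14] = sqrt(1.667/14) = 0.345 day.

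A simulation of 20,000 order lists gave 0.490 and 0.343.

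**4. Effect on the CC-FII estimate.** With no day effect the standard error is sqrt(2/28) = 0.267 SD. A drift of d SD per day has two effects:

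- the estimate shifts by a random amount with mean 0 and SD 0.345d;
- the expected residual variance of the condition-only model becomes 1 + (5/3)d², because the squared deviations of days 1-4 sum to 5 on 3 df.

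| Drift d (SD/day) | SD of shift | SE without day: 0.267 x sqrt(1 + 5d²/3) |
|---|---|---|
| 0.25 | 0.09 | 0.28 |
| 0.5 | 0.17 | 0.32 |
| 1.0 | 0.345 | 0.44 |

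With day in the model the simulated SE is about 0.28 at every drift.

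**5. Power for a true effect of 0.8 SD** (3,000 simulated trials per scenario, random orders):

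| Drift (SD/day) | Without day | With day |
|---|---|---|
| 0 | 82% | 79% |
| 0.25 | 81% | 81% |
| 0.5 | 69% | 79% |
| 1.0 | 44% | 79% |

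Separate runs agreed to within about 2 points.

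**6. Type I error.** Over all random lists it is about 5% in both models at every drift. The excess is confined to unlucky lists. Where FII and CC differ by at least 8/14 = 0.57 day on average (11-12% of lists), a drift of 0.5 SD per day gave 15-17% without day in separate runs and about 5% with it.

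**7. If the orders were near-balanced** (Williams blocks cut off at 14), the shift at 0.5 SD per day is at most 0.11 SD. The unadjusted test then becomes conservative, with type I error 2.6%. Power is 73% without day and 83% with it. Good balance removes most of the shift but not the loss of power.

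**The case against.** - **No day effect is shown.** This stands. The drifts are assumptions, and at 0.25 SD per day or less omitting day does little harm. The design also limits plausible causes: meals are prepared and delivered, doses follow fixed formulas, and the evening snack, fast and start time are standardised. Sensor age can affect only CGM values, and Section 6 does not say whether CGM or glucometer readings feed the AUC. A reader might infer from the insertion timing or the lack of a washout day that a day effect or carry-over is present. The documents give only the opportunity for one.
- **Randomised order already protects the comparison.** This stands on average over possible lists. It does not protect the single list used, and it does not recover the lost precision.
- **14/4 = 3.5 does not unbalance CC against FII.** This stands. A reader might take the fraction as proof that the algorithm comparison is unbalanced, but a 7:7 split per day is possible and the list is not shown. Simple random permutation is itself an assumption.
- **A day term is not always cheap.** This is the strongest point. The comparable conditions in Section 6 might mean separate pairwise analyses, such as high GI under CC against high GI under FII. Each would then have 27 - 13 - 1 = 13 residual df, or 10 with day. A simulation of that case (assumed effect 1.1 SD) gave power without and with day of 76% and 63% at no drift, 73% and 63% at 0.25, and 62% and 64% at 0.5 SD per day. Adding day to separate pairwise models would therefore lose power over much of the range. The remedy has to be one joint model.

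**Conclusion.** The point holds in a limited form. The plan randomises order over four consecutive days and omits day from the analysis. If a day effect exists, the main cost is power: about 10 points at an assumed drift of 0.5 SD per day and 35 at 1.0. There is also a chance, depending on the list used, of a shift in the CC-FII estimate. At 0.25 SD per day or less the harm is small.

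A reader might go further and conclude that day is confounded with algorithm, or that the planned test is biased. The documents do not support that: the order is random, the expected shift is zero, and average type I error is near 5%.

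The case for acting is the asymmetry within a joint model: 2-3 points of power lost if there is no drift, 10 or more gained if drift is substantial. This rests on complete AUCs, a common linear drift and a 0.8 SD effect, none of which the documents supply.

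**What to change.** Replace the t-tests and one-way analysis of the test conditions by one model for the AUCs from all four conditions. Include participant (fixed or random), algorithm, GI, algorithm x GI, and test day as a four-level fixed effect. Take the CC-FII contrasts, overall and within each GI level, from that model rather than from separate pairwise models. State how the order list was generated, and tabulate the number of participants on each condition by day.

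The cost is a change of SAP wording and 3 residual df (39 to 36 with 56 complete AUCs), or about 2-3 points of power if day has no effect. The residual df will be lower if post-hypoglycaemia exclusions leave AUCs missing. The day of each test follows from the order list, so no new data are needed. Rebalancing the sequences looks too late, since the list was fixed before recruitment. If the AUCs have already been compared, report the day-adjusted result beside the planned one and label it as added later.

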## **2. Objective**

The aim of this study is to compare the impact of carbohydrate counting (CC) method which is standard insulin dose calculation algorithm and food insulin index (FII) method which is a new algorithm on postprandial glucose following high fat and high protein meals with different GIs in adolescent with type 1 diabetes.

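### Every analysis is judged at p<0.05 with no primary outcome, contrast, glucose source or multiplicity control, so the plan permits (but does not prescribe) up to 96 tests at that level

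*Combined protocol and SAP*

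**What the plan says.** Section 6 (Statistical Analysis) gives a single decision rule: "For all statistical analyses, p values less than 0.05 were considered to have statistical significance". It names two kinds of test. One is a t-test: "Differences between groups were tested using t-tests". The other is a one-way repeated-measures analysis of the conditions it regards as comparable, without saying which those are. Neither test is made conditional on the other, and no post-hoc procedure is given. The same section summarises the 4-hour glucose profile by a trapezoidal AUC but does not call it primary.

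The objective (section 2) is the effect of the two dosing algorithms "on postprandial glucose following high fat and high protein meals with different GIs", with no endpoint or time named.

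Section 3.1 defines four conditions in 14 adolescents: each algorithm with a high-GI and a low-GI breakfast (CHGI, CLGI, FHGI, FLGI).

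Section 4 states that "Postprandial glycemia was measured for 240 min with both continuous glucose monitoring and glucometer". It schedules capillary tests before the meal and "at time points 30, 60, 90, 120, 150, 180, 210 and 240 min after the meal with glucometer". It does not say which source feeds the analysis.

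**The concern.** A threshold of 0.05 per test gives a 5% error rate for the trial's conclusion only if one test carries that conclusion. Here the outcome can be read as an AUC or as the glucose value at any of eight times, from either of two sources, across any of six pairs of conditions. Once more than one of these is read at 0.05, the stated rule no longer holds 5%. A report that FII outperforms CC at one time, on one breakfast or with one device could then arise readily by chance, and nothing in the plan tells a reader which result was meant to count.

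**Working it through.** The documents give no power calculation and no familywise error rate, so there is no planned figure to reproduce.

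**Inputs from the documents**
- Level per test: 0.05 (section 6). Sidedness is not stated; two-sided is assumed.
- Conditions: 4 (section 3.1), so pairs = 4 × 3 / 2 = 6. Two pairs compare CC with FII on the same breakfast: CHGI v FHGI and CLGI v FLGI. Of the other four, two vary GI alone and two vary GI and algorithm together.
- Post-meal times: 8, stated for the glucometer (section 4).
- Glucose sources: 2 (section 4).
- Participants: 14, each in all four conditions (section 3.1), so a paired t-test has 13 degrees of freedom.

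**Inputs not in the documents (assumed)**
- Correlation between adjacent times 0.70 to 0.95, first-order autoregressive.
- Correlation between the two sources 0.85.

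**Largest number of tests left open:** 6 × 8 × 2 = 96.

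**Independence figures,** 1 − 0.95^k for k tests:
- k = 2: 9.8%
- k = 6: 26.5%
- k = 48: 91.5%
- k = 96: 99.3%

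These should not be used as estimates, because the tests share the same 14 participants, neighbouring times and pairs with a condition in common.

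**Simulation under no true difference.** For each trial, generate 14 participants × 4 conditions × 8 times × 2 sources with the correlations above. Apply two-sided paired t-tests at 0.05, and take AUC as the mean of the eight post-meal values. Record whether any test in the set is significant.

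| Set of tests | One source | Both sources |
|---|---|---|
| One overall repeated-measures test of AUC | about 5% | 6–9%* |
| AUC, two same-meal CC v FII pairs | 9–10% | 14–16% |
| AUC, all six pairs | 21–23% | about 30% |
| Eight times, two same-meal CC v FII pairs | 24–45% | 34–60% |
| Eight times, all six pairs | 45–73% | 60–86% (all 96 tests) |

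*Source correlation 0.70 to 0.95, time correlation 0 to 0.95. Over those wider ranges the 96-test figure runs from 55% to 96%.

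If pairwise AUC tests were read only after a significant overall test, the rate would stay where the first row puts it. The plan states no such condition.

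Counting only false results in favour of FII, the two same-meal pairs at eight times give about 12–25% on one source and 18–35% on both.

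**The case against.** The strongest reply is that the plan's analysis is narrower than the grid. Section 6 summarises the profile as an AUC and applies a repeated-measures test to it. The eight fingerstick times can be read simply as inputs to that AUC. On this reading the error rate is about 5% on one source. Much of this stands: section 6 does not say that all six pairs, each time point or both sources are tested.

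A reader might therefore infer too much in three ways.
- **That 96 tests are planned and a false positive is likely.** The documents leave the grid open and do not prescribe it. Above-even odds hold for the full grid. They do not hold for AUC alone.
- **That a spurious FII advantage is to be expected.** For same-meal CC v FII tests at eight times on one source the figure is 24–45% in either direction, below one half. The largest figures count four pairs that compare breakfasts of different GI. Table 1 gives GIs of 64 and 35, so assuming no difference there is doubtful, and an error in a pair differing only in GI is not a claim about the algorithm.
- **That the answer is 99.3%.** That requires independent tests.

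The narrow reading is not secured by the text, however. The t-tests stand in their own sentence, ungated. There are no parallel arms, so the natural meaning of groups is the four conditions. Section 4 drops readings after a hypoglycaemic event, which works at the level of time points and can leave an incomplete 4-hour AUC, so time-point analysis is realistic. The glucose source is open under either reading.

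**Conclusion.** The concern holds as a lack of control. One threshold applies to everything, the t-tests are ungated, and no primary outcome, contrast, source or adjustment is named. The false-positive risk therefore depends on choices the plan leaves free: about 5% for one overall AUC test, 9–23% for unadjusted AUC pairs on one source (14% to about 30% on both), 24–45% for same-meal CC v FII tests at eight times on one source, and 60–86% if everything is tested. It should be corrected, but it does not show that the trial will produce a false claim.

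The simulated sizes rest on two-sided tests, no true difference between any conditions, and the assumed correlations. The time-point figures are the most sensitive to correlation; the one-source AUC figures barely move with it.

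**What to change.** In section 6:
1. Name one primary test at two-sided 0.05: the CC–FII main effect on 4-hour AUC. Per participant this is the mean of CHGI and CLGI minus the mean of FHGI and FLGI. It needs a two-factor (algorithm × GI) within-subject model in place of the one-way analysis. Simulated error for this single test is 4–5%.
2. Name one glucose source for it before results are examined, with the other as a sensitivity analysis. CGM is a reasonable choice because it does not rely on nine fingersticks at home, but the documents favour neither; what matters is that the choice is fixed.
3. Test the algorithm × GI interaction second.
4. Adjust the two same-meal CC v FII contrasts by Holm: the smaller p-value against 0.05 / 2 = 0.025 and, if that passes, the larger against 0.05.
5. Report individual time points with 95% confidence intervals and no significance claims.

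The cost is a small change of model, some SAP wording and fewer nominally significant secondary results. Meals, doses and schedule are unaffected. The documents are written in the past tense and do not show whether data had been seen. If they had, naming a primary test now would not restore error control, and the pairwise and time-point results should be labelled exploratory.
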